4. INVESTIGATIONAL PLAN

4.1. Overall Study Design

This is a Phase 2, randomized, double-blind, placebo-controlled, 2-arm multicenter study to assess the safety and efficacy of oral STI-5656 (or placebo) in the setting of current SOC in subjects with RT-PCR confirmed SARS-CoV-2 infection and COVID-19 pneumonia (documented radiographically) requiring hospitalization. Subjects must have oxygen saturation levels <94% on room air or subject requires supplemental oxygen.

Eighty (80) subjects meeting eligibility criteria will be randomized at a 1:1 ratio to one of two treatment arms in addition to SOC treatments:

- Arm 1: STI-5656
- Arm 2: Placebo

The STI-5656 dose is 100 mg p.o. QD administered up to 14 days or until hospital discharge if sooner.

SOC treatments will be collected in the electronic case report form (e-CRF).

Subjects who discontinue at any time after randomization will not be replaced. There is no treatment crossover in this study.

Once subjects provide informed consent, they will have screening assessments performed (up to 4-day screening window). Study Day 1 is the day of randomization. Randomized Subjects should receive their first dose of Study Drug on Day 1.

Subjects will be assessed daily while hospitalized. Subjects in both arms are assessed for adverse events (AEs) and toxicities and all AEs should be reported regardless of treatment arm assignment or causality. Subjects will be contacted on Day 28 to collect any additional AEs and follow-up for unresolved AEs,

SOC treatments will be collected in the electronic case report form (e-CRF) until hospital discharge. Continued outpatient treatment (concomitant medications) will be collected until Day 28. Any investigational medication received will be collected until Day 90. Note: Investigational medicines other than STI-5656 are prohibited up to Day 28 or hospital discharge.

Discharged subjects will be contacted at Day 60 and 90 to ensure survival and collect any experimental treatments and additional hospitalization information since the study hospital discharge. Subjects on Treatment Arm 1 (STI-5656) should be encouraged to remain in the study even if Study Drug is discontinued (for any reason).

An independent data monitoring committee (DMC) is established to evaluate the safety data from the study to ensure the ongoing safety of the study subjects and make recommendations to the Sponsor concerning safety and trial conduct (please refer to the DMC charter for details). A blinded independent statistician will be used to facilitate DMC support. This statistician will have no role in the statistical assessments conducted for the study at its conclusion. Discussions with the independent statistician will be conducted during a closed session during the DMC deliberations. Sponsor, CRO and study site personnel will only participate in the open session.

Unblinding of a given subject to assess an AE stopping rule trigger will be handled in a way to keep the Sponsor, CRO (and staff) and study site personnel blinded.

The study visit schedule and assessments are detailed in [Table 1](#) Schedule of Assessment (SOA).

For subjects, the total duration of the study will be up to 94 days (up to 4 days for the screening period plus up to 14 days for treatment and up to 90 days from randomization for follow-up).

The length of the study will be approximately 7 months (4 months for enrollment plus up to 90 days study duration).

4.2. End of Trial Definition

The End of Trial is defined as either the date of receipt of the last data point from the last subject that is required for primary, secondary and/or exploratory analysis, as prespecified in the protocol, whichever is the later date.

5. SELECTION AND WITHDRAWAL OF SUBJECTS

Prospective approval of protocol deviations to recruitment and enrollment criteria, also known as protocol waivers or exemptions, is not permitted.

Subjects who are randomized but discontinue prior to the end of the study will not be replaced.

5.1. Subject Inclusion Criteria

Subjects are eligible to be included in the study only if all the following criteria apply:

1. Confirmed infection with SARS-CoV-2 per World Health Organization (WHO) criteria (including positive RT-PCR nucleic acid test of any specimen [eg, respiratory, blood, urine, stool, or other bodily fluid]) within 7 days of randomization. Positive RT-PCR test results more than 7 days prior to randomization is allowed if the site is unable to obtain a repeat sample and if the subject has progressive disease consistent with COVID-19.
2. COVID-19 pneumonia (documented radiographically) requiring hospitalization and oxygen saturation <94% on room air or subject requires supplemental oxygen.
3. Age ≥ 18 years at the time of signing the informed consent form
4. Subject or family member/caregiver must have provided written informed consent which includes signing the institutional review board approved consent form prior to participating in any study related activity. However, if obtaining written informed consent is not possible, other procedures as provided in the March 27th, 2020 FDA Guidance on Conduct of Clinical Trials of Medical Products during COVID-19 Pandemic, Question 10, may be used.
5. Able to swallow capsules
6. Willing to follow contraception guidelines

If a female, be sterile (surgically or biologically)* or at least one year post-menopausal**, or have a monogamous partner who is surgically sterile, or have a same sex partner, or if in a heterosexual relationship, must agree to do the following for at least 1 month after receiving IP:

- Practice abstinence
- Use at least 1 of the following medically acceptable methods of birth control:
 - Hormonal methods such as oral, implantable, injectable, vaginal ring, or transdermal contraceptives (must have started a minimum of 1 full cycle, based on the subject's usual menstrual cycle period, before IP dose)
 - Intrauterine device
 - Double-barrier method (condoms, sponge, or diaphragm with spermicidal jellies or cream).

**Defined as having had a hysterectomy and/or bilateral oophorectomy, bilateral salpingectomy or bilateral tubal ligation/occlusion at least 6 weeks prior to screening; or having a congenital or acquired condition that prevents childbearing*

***Defined as at least 12 months with no menses without an alternative medical cause)
[can be confirmed with follicle stimulating hormone level (FSH) in the post-menopausal range (FSH levels ≥ 40 milli international units/mL (mIU/mL) at Screening) if the subject is not on hormonal replacement therapy]*

If a male of reproductive potential*, unless he has a same sex partner, must agree to do the following for at least 1 month after receiving IP

- practice abstinence from heterosexual activity, or
- use (or have their partner use) acceptable contraception (see criterion above) during heterosexual activity

*Defined as having azoospermia, whether due to having had a vasectomy or due to an underlying medical condition.

5.2. Subject Exclusion Criteria

Subjects are excluded from the study if any of the following criteria apply:

1. Known cardio-pulmonary resuscitation within 14 days of randomization
2. Pregnant or breast feeding
3. Suspected uncontrolled active bacterial, fungal, viral, or other infection (besides infection with SARS-CoV-2)
4. Alanine aminotransferase (ALT) $\geq 3x$ upper limit of normal (ULN) and total bilirubin $> 2x$ ULN
5. QTcF prolongation >480 milliseconds
6. Uncontrolled or untreated symptomatic arrhythmias, myocardial infarction within the last 6 weeks, or congestive heart failure (NYHA Grade 3 or 4). Exception: Subjects with controlled, asymptomatic atrial fibrillation during screening are allowed to enroll
7. Treatment with a strong cytochrome P450 (CYP3A4 inhibitor (within 14 days before first dose of study drug) or inducer (within 7 days before first dose of study drug).
8. Received anti-rejection or immunomodulatory drugs (eg, anti-cytokines, BTK inhibitors, JAK inhibitors, PI3K inhibitors) within 30 days before randomization on study
9. Concurrent participation in another clinical trial involving therapeutic interventions (observational study participation is acceptable).
10. Any condition that confounds the ability to interpret data from the study.
11. Relevant renal impairment (eGFR <60 ml/min)
12. Any significant medical condition, laboratory abnormality or psychiatric illness that would interfere or prevent the subject from participating in the study.

5.3. Screen Failures

Screen failures are defined as subjects who consent to participate in the clinical study but are not subsequently entered in the study. A minimal set of screen failure information is required to

ensure transparent reporting of screen failure subjects to meet the Consolidated Standards of Reporting Trials (CONSORT) publishing requirements and to respond to queries from regulatory authorities. Minimal information includes demographics, screen failure details, eligibility criteria, and any SAE.

Individuals who meet all the screening criteria but were not selected for cohort may be re-screened to participate in a subsequent cohort. Screening laboratory tests and/or vital signs may be repeated once if, in the opinion of the Investigator, the out-of-range values are thought to be spurious and not indicative of an underlying disease or abnormality.

6. TREATMENT OF PARTICPANTS

6.1. Description of Investigational Product

Study treatment will be either STI-5656 (Investigational Product, or IP) or placebo.

6.2. Investigational Product Administration

Two STI-5656 or matching placebo capsules p.o. QD (two 50-mg capsules) administered up to 14 days or until hospital discharge if sooner.

Study drug capsules should be taken orally with 200-250 mL of water following at least 2 hours of fasting.

If vomiting occurs within 30 minutes after a patient takes the dose and the patients can tolerate the medication, the vomited dose should be made up.

If the subject is unable to swallow, the capsule contents may be flushed down a nasogastric or feeding tube with water.

6.3. Stopping Rule Triggers

Study drug dose should be paused per the guidelines in [Table 2](#) (using the Common Terminology Criteria for Adverse Events, Version 5.0 [CTCAE] for severity grading).

Table 2: Stopping Rule Triggers

If any of the following possibly related AEs occur:	At the first occurrence of any of the stopping rule triggers, discontinue Study Drug for the affected subject and pause further enrollment until DMC deliberations have been completed and a DMC decision that enrollment may be restarted has been rendered.

 • \geq Grade 3 (G3) non-hematologic toxicities • \geq G3 alanine aminotransferase (ALT) elevation OR \geq any ALT and total bilirubin elevation in combination which meet Hy's Law criteria [i.e., any \geq G3 hepatic impairment] • G3 thrombocytopenia with bleeding • G4 thrombocytopenia • G4 neutropenia • G3 neutropenia or thrombocytopenia in > 3 subjects • \geq G3 renal impairment including acute kidney injury requiring hemodialysis • Any SUSAR (suspected unexpected serious adverse reaction) 	

A DMC teleconference will be arranged within 5 business days of the stopping rule trigger. This should provide sufficient time for the CRO to prepare a blinded summary of the AE and the independent statistician to arrange to be unblinded to assist the DMC in its deliberations.

Additionally, the DMC will be provided with tabular safety summaries at 25%, 50% and 75% enrollment for ongoing surveillance.

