10.2.3. Causality

An Investigator who is qualified in medicine must make the determination of relationship to the investigational product for each AE (Unrelated, Possibly Related or Probably Related). The Investigator should decide whether, in his or her medical judgment, there is a reasonable possibility that the event may have been caused by the investigational product. If no valid reason exists for suggesting a relationship, then the AE should be classified as “unrelated.” If there is any valid reason, even if undetermined, for suspecting a possible cause-and-effect relationship between the investigational product and the occurrence of the AE, then the AE should be considered “related.”

If the relationship between the AE/SAE and the investigational product is determined to be “possible” or “probable” the event will be considered to be related to the investigational product for the purposes of expedited regulatory reporting.

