10.2.5. Action Taken

The Investigator will report the action taken with investigational product as a result of an AE or SAE, as applicable (e.g., discontinuation, interruption, or reduction of study treatment, as appropriate) and report if concomitant and/or additional treatments were given for the event.

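### Protocol Section 6.3 says to pause study drug while its own Table 2 says to discontinue it, and the scope of first occurrence is not stated for the drug action or the enrollment pause

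*Protocol*

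**What the plan says.** Protocol Section 6.3 opens with "Study drug dose should be paused per the guidelines in" Table 2. The table's condition is "If any of the following possibly related AEs occur", followed by a list of toxicities. Its single action cell reads "At the first occurrence of any of the stopping rule triggers, discontinue Study Drug for the affected subject and pause further enrollment", and the enrollment pause lasts "until DMC deliberations have been completed and a DMC decision that enrollment may be restarted has been rendered".

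Most triggers on the list are events in one subject. One is a count over the trial: "G3 neutropenia or thrombocytopenia in > 3 subjects". Below the table the section adds "A DMC teleconference will be arranged within 5 business days of the stopping rule trigger".

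Protocol Section 10.2.5 asks the investigator to record the action taken with the product and gives as examples "discontinuation, interruption, or reduction of study treatment, as appropriate".

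The SAP has no text on toxicity stopping. Its Section 8.6 summarizes days on treatment, dose planned, administered and missed, and compliance as administered over planned dose.

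**The concern.** A site that meets a trigger has to know whether the subject's drug is held or stopped for good, and whether the instruction applies each time. Section 6.3 answers the first question in two ways and leaves the second open. Two sites acting in good faith on the same event could do different things, and each could point to text in the same section.

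The first stake is safety, because this is an instruction that sites must carry out in the same way. The second is trial conduct, since the same phrase decides how often enrollment halts. The third is interpretation of exposure: days on drug and compliance could differ between subjects because of which sentence was followed and not because of their clinical course.

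**Working it through.** No figure in the documents is at issue, so the check is mainly a comparison of text.

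**Step 1. The drug action.**

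| Place | Study drug | Enrollment | Restart condition |
|---|---|---|---|
| Section 6.3, opening sentence | paused | not mentioned | none |
| Section 6.3, Table 2 | discontinued | paused | DMC decision, for enrollment only |

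Section 10.2.5 names interruption and discontinuation as separate actions, so the two words cannot be taken as synonyms within this protocol. If the opening sentence governs, nothing says when a paused dose may resume. If the table governs, the sentence is wrong. No other protocol section and no part of the SAP settles it.

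**Step 2. The scope of first occurrence.** The phrase stands before both actions. Linking two actions to one event is not in itself a contradiction. What is missing is the unit in which first is counted.

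| First is counted per | Later subject, same trigger, after restart: drug | Same subject: enrollment |
|---|---|---|
| trial | no action stated in Table 2 | no action stated in Table 2 |
| trigger type | no action stated in Table 2 | no action stated in Table 2 |
| subject | discontinued | paused again |

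A fourth reading, with the drug action per subject and the enrollment pause per trial, is also possible. The single phrase does not provide for it.

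**Step 3. The cross-subject trigger.** The count is met when a fourth subject has the event. The action then falls on the affected subject, in the singular. Table 2 does not say whether that is the fourth subject only or all four, nor what applies to the first three if they are still on drug.

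**Step 4. Would later occurrences arise?** The documents give no trigger rate. For illustration only, assume a per-subject probability p common to all N = 80 planned subjects and independent between them:

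- P(at least one subject) = 1 − (1 − p)^80
- P(at least two) = 1 − (1 − p)^80 − 80p(1 − p)^79
- Expected subjects beyond the first = 80p − P(at least one)

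| Assumed p | P(at least one) | P(at least two) | Expected beyond the first |
|---|---|---|---|
| 2% | 80.1% | 47.7% | 1.6 − 0.801 = 0.8 |
| 5% | 98.3% | 91.4% | 4.0 − 0.983 = 3.0 |
| 10% | 99.98% | 99.8% | 8.0 − 1.000 = 7.0 |
| 20% | >99.99% | >99.99% | 16.0 − 1.000 = 15.0 |

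Even at 2%, a second affected subject is close to an even chance, so the missing instruction for later occurrences is not a remote case. The table shows nothing about how often triggers will in fact occur.

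**Step 5. What the analysis would feel.** Protocol Section 9.4.3 and SAP Section 9.1 count leaving the study before Day 28 as failure. They do not count stopping the drug. The synopsis encourages subjects to stay in the study after drug is stopped. The rule for the primary endpoint is therefore untouched. The SAP Section 8.6 summaries do depend on the action taken. Planned dose is not defined there, so whether it keeps accruing after a pause or ends at discontinuation is open, and compliance moves with it.

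**The case against.** The strongest reply is that the opening sentence defers to Table 2, so *paused* is a loose lead-in and the table is the operative rule. That is a fair guess at the intent, but the text does not say so, and Section 10.2.5 keeps the two actions apart. It would also leave Steps 2 and 3 unanswered.

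Other parts of the reply stand, and they limit the point:

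- A reader might infer that Table 2 is the only route for acting on toxicity. It is not. The introduction to Section 8 has immediate safety concerns discussed with the sponsor to decide whether the subject stays on drug, and Section 10.2.5 foresees action on the product because of an adverse event. *No stated action* is true of Table 2 only.
- A reader might infer that only one subject in the whole trial would ever be taken off drug. The wording allows this, but it is the least natural reading, since the condition is triggered by any listed event and the action attaches to the affected subject.
- A threshold of more than three means that three do not trigger. That is how thresholds work, and it is not an error. Who keeps the count may be set out in the DMC charter, which is not available here. The open question is only how the action applies to individuals once the count is met.
- A reader might infer that probably related events are exempt, because Section 10.2.3 lists "Unrelated, Possibly Related or Probably Related" and Table 2 names only the middle category. That section treats both the possible and the probable category as related, and a minimum level is the ordinary reading. This is not part of the point.

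**Conclusion.** Section 6.3 is wrong as written on one matter and incomplete on two. The contradiction is pause against discontinue for study drug. The omissions are the unit of first occurrence, which governs both a subject-level and a trial-level action, and the application of a cross-subject count to individual subjects. Together they mean that equal events *can* be handled differently across sites. The documents do not show that they will be.

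The size is unknown, because no trigger rate is given. The illustration rests on assumed rates of 2% to 20%, equal across subjects and independent.

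Two stronger conclusions are tempting and should not be drawn. One is that repeated pauses would consume much of the planned four months of enrollment. That needs an assumed event rate, the full five business days at each trigger and no overlap between pauses, whereas the protocol sets five days as an upper limit for the DMC call. The other is that pause and discontinuation differ only for triggers early in the 14 dosing days. That needs the same full wait and a drug restart tied to the DMC decision, which the text ties to enrollment alone.

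The effect is on subject safety, on the number of enrollment pauses and on descriptive exposure and compliance. The primary endpoint rule is not affected.

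**What to change.** The sponsor should amend Section 6.3 so that the opening sentence and Table 2 state one and the same action on study drug. The amended text should then state, separately for the drug action and for the enrollment pause:

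1. what first occurrence refers to (subject, trigger or trial);
2. what applies to later occurrences;
3. how the trigger counted over more than three subjects applies to individual subjects, including those counted before the threshold is reached.

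The choice of action in each case is the sponsor's, and no view is given on it here.

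The cost is one section and one table revised in the next amendment and sent to the sites and the DMC. It needs no added data and no added subjects.

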6.4. Dosing of Subjects Unable to Take Test Article PO

Subjects unable to take the capsules PO, for example after intubation may receive the drug or placebo via feeding tube. The formulation is blended powder filled in capsule allowing for

opening the capsules and dosing the content as is with water to flush the feeding tube. If this is not feasible, dosing should be discontinued.

6.5. Investigational Product Compliance

Subjects receive IP only while hospitalized and it is administered at the site; therefore, the site will monitor IP compliance.

6.6. Overdose

Any dose over the protocol-specified daily dose of STI-5656 will be considered an overdose. The Sponsor does not recommend specific treatment for an overdose.

In the event of an overdose, the Investigator should:

- Contact the Medical Monitor immediately.
- Closely monitor the subject for any AE/SAE for at least 24 hours.
- Document the quantity of the excess dose.

6.7. Randomization and Blinding

Screening, randomization to one of two treatment arms (1:1 ratio), as well as study completion or study discontinuation will be registered by the site using an IRT system.

6.8. Emergency Unblinding

Emergency unblinding may be requested by the Investigator at any time if needed to properly assess the patient. The request should be submitted to the CRO and Sponsor's medical monitor.

6.9. Concomitant Medications

Any medication (including over the counter or prescription medicines, vitamins, and/or herbal supplements), vaccine or transfusion that the subject received within 28 days prior to the Screening Visit and during the study up to hospital discharge must be recorded along with:

- Reason for use
- Dates of administration including start and end dates
- Dosage information including dose and frequency

The Medical Monitor should be contacted if there are any questions regarding concomitant or prior therapy.

6.9.1. Prohibited Concomitant Medications

The following medications are prohibited up to Day 28 or hospital discharge:

Anti-cytokines, other BTK inhibitors or other tyrosine kinase inhibitors (e.g. JAK or PI3K inhibitors as well as any immunosuppressive drugs (except steroids), such as anti-IL6 or anti-TNF α therapy.

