8. STUDY PROCEDURES

Study procedures will be performed as described in the Schedule of Assessment [Table 1](#).

Additional unscheduled visit/assessments may be performed at any time if clinically indicated and will be captured in the eCRFs if performed.

Protocol waivers or exemptions are not allowed, with the exception of immediate safety concerns. Such concerns should be discussed with the Sponsor immediately upon occurrence or awareness to determine if the subject should continue or discontinue the IP (subjects in Treatment Arm 1). Adherence to the study design requirements, including those specified in the Schedule of Assessments, is essential and required for study conduct.

All screening evaluations must be completed and reviewed to confirm that potential subjects meet all eligibility criteria. The Investigator will maintain a screening log to record details of all subjects screened and to confirm eligibility or record reasons for screening failure, as applicable.

A subject may be re-screened once for the study if the defined screening period has been exceeded and the subject has not been randomized in the study.

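### Protocol V4.0 bars CYP3A4 inhibitors (strong) and inducers shortly before first dose, but its on-treatment prohibited list leaves them out

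*Protocol*

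**What the plan says.** **At entry.** Protocol Section 5.2, criterion 7, excludes "Treatment with a strong cytochrome P450 (CYP3A4 inhibitor (within 14 days before first dose of study drug) or inducer", with a 7-day window for the inducer. Criterion 8 excludes patients who "Received anti-rejection or immunomodulatory drugs (eg, anti-cytokines, BTK inhibitors, JAK inhibitors, PI3K inhibitors) within 30 days before randomization on study".

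**On treatment.** Section 6.9.1 prohibits, up to Day 28 or discharge, "Anti-cytokines, other BTK inhibitors or other tyrosine kinase inhibitors (e.g. JAK or PI3K inhibitors as well as any immunosuppressive drugs (except steroids", with anti-IL6 and anti-TNF-alpha therapy as examples. The synopsis and Section 4.1 add one further ban, on other investigational medicines.

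**Dosing.** Under Section 6.2 study drug is "administered up to 14 days or until hospital discharge if sooner". Section 6.5 adds: "Subjects receive IP only while hospitalized and it is administered at the site".

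**General safeguards.**
- Section 6.9: "The Medical Monitor should be contacted if there are any questions regarding concomitant or prior therapy".
- Section 8, where safety is urgently at issue: "Such concerns should be discussed with the Sponsor immediately upon occurrence or awareness to determine if the subject should continue or discontinue the IP".
- Section 6.3, for listed possibly related adverse events: "At the first occurrence of any of the stopping rule triggers, discontinue Study Drug for the affected subject and pause further enrollment".
- Section 8.2.3: vital signs, laboratory tests, adverse events and concomitant medications are reviewed daily in hospital.

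**SAP.** Section 8.4 lists all medications. Section 8.5 has deviations reviewed before database lock. Section 1.0 states that the plan is based on protocol V5.0 and leaves PK analysis to another document.

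**The concern.** The sponsor regards recent use of these drugs as sufficient reason to refuse a patient. The exclusion is timed from first dose, whereas criterion 8 is timed from randomisation, and that timing fits a worry about overlap with study drug. If so, a rule that protects the first dose and then lapses does not serve its purpose.

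Subjects receive standard of care in hospital while they are being dosed, so new prescriptions during the dosing period are foreseeable. A prescriber who checks Section 6.9.1 finds nothing against a strong CYP3A4 inhibitor or an inducer and has no prompt to ask. What is at stake is the safety of the individual subject who is given one. No part of the primary inference is at stake.

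**Working it through.** The point is textual. The plan gives no figure for it, so the check is to set the rules for each drug group side by side.

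| Drug group | Before first dose or randomisation | During dosing |
|---|---|---|
| Strong CYP3A4 inhibitor | Excluded if within 14 days of first dose (5.2, criterion 7) | Not mentioned |
| CYP3A4 inducer | Excluded if within 7 days of first dose (5.2, criterion 7) | Not mentioned |
| Anti-cytokines; BTK, JAK and PI3K inhibitors | Excluded if within 30 days of randomisation (5.2, criterion 8) | Prohibited (6.9.1) |
| Other investigational medicines | Concurrent therapeutic trial excluded (5.2, criterion 9) | Prohibited (synopsis, 4.1) |

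1. *Is there a CYP3A4 rule elsewhere?* No. Criterion 7 is the only mention of CYP3A4 in the protocol or the SAP, and it ends at first dose.

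2. *Does the list otherwise follow the exclusions?* Yes. Section 6.9.1 takes the named classes of criterion 8 into the treatment period. It does not do the same for criterion 7, and no reason is given.

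3. *Could another ban catch these drugs?* Only in part. A drug that also belongs to a listed class, or is investigational, stays barred on that ground. A marketed strong CYP3A4 inhibitor or inducer outside those classes does not.

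4. *Does another rule require a hold?* No. Medical Monitor contact depends on the site having a question. Discussion with the sponsor depends on an immediate safety concern. The stopping rule depends on a possibly related adverse event or a SUSAR. Daily review may detect an effect but does not prevent it. None of these is triggered by the prescription itself.

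5. *How far does the gap reach?* It covers the dosing period, at most 14 days per subject. With 80 subjects randomised 1:1, 80 / 2 = 40 are planned for STI-5656, and only they can be exposed to an interaction. This counts who could be affected and for how long. It is neither a risk nor an effect size, because the documents give no interaction data and no rate of use.

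**The case against.** The strongest reply is that the text may be out of date and that harm has not been shown. The SAP rests on protocol V5.0, which is not available here. Neither document says that STI-5656 is a CYP3A4 substrate, and the Investigator Brochure is not available either. Dosing takes place in hospital under daily review, with a Medical Monitor to call. All of this stands. It limits the finding to V4.0 and lowers its weight, but it does not supply the missing rule.

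Four stronger readings are tempting, and the documents do not support them.

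- *The Day 8 PK profile is compromised.* A reader might infer this because PK is sampled on dosing days 1 and 8 in the first 20 subjects. But Section 6.9 already has medication start and end dates recorded, and the PK analysis is planned elsewhere. Nothing shows that overlap would be missed.
- *The 14-day and 7-day windows can be applied at Day 8 to give a percentage uncovered.* These windows are defined before first dose. Moving them to a later dose uses an entry rule at a time it was not written for and measures neither exposure nor risk.
- *Such use would not count as a deviation.* Neither document defines a deviation, and SAP Section 8.5 leaves classification to review. The text supports only the narrower statement that no listed prohibition is breached.
- *All CYP3A4 inducers should be banned.* Section 6.9.1 expressly allows steroids, and the documents do not say which drugs count as inducers. An unqualified ban could conflict with that allowance.

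**Conclusion.** The gap is real in the V4.0 text. A site that follows the protocol exactly may start, during up to 14 days of dosing, a drug whose recent use would have kept the patient out, and nothing requires it to hold study drug.

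The conclusion on the wording is firm. Its clinical relevance is an inference from the sponsor's own criterion 7. The direction and size of any change in exposure, and the number of subjects who would be given such a drug, cannot be told from the documents. Whether V5.0 has the same gap is unknown.

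This is a cheap improvement on patient-safety grounds. The sample-size inputs, the primary model, the significance level, randomisation and blinding are all untouched.

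**What to change.** First check Section 6.9.1 of protocol V5.0. If it has not closed the gap:

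- Add strong CYP3A4 inhibitors and strong CYP3A4 inducers to Section 6.9.1 for the dosing period, ending at the earlier of Day 14 and discharge. Apply the rule to both arms, because sites are blinded.
- State in the same place that steroids remain allowed, as the section already provides.
- If such a drug becomes clinically necessary, require contact with the Medical Monitor, who decides whether study drug is held or stopped. An automatic hold is not recommended: it withdraws treatment from the subject, and the documents do not show that this is better than continuing.
- Optionally, flag dosing days that overlap such a drug, using the recorded medication dates.

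The cost is one amendment with IRB/IEC re-approval (Section 13.1) and possibly some additional deviations or dose holds; their number cannot be estimated without a rate of use. No new data are needed. A subject whose study drug is held stays in the full analysis set, which includes everyone randomised. A newly listed prohibition could remove some subjects from the per-protocol population, which serves only sensitivity analysis.
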